Official Title of the study: **Effect of Varied Outreach Methods on Appointment Scheduling, Appointment Completion, and Receipt of MMR Vaccination**

NCT number: **NCT04567342**

Document name: **Study Protocol**

Date of the document: **12/1/21**

Redesigning Outreach Post-COVID-19 in Academic Pediatric Primary Care

[name], MS
Professor of Pediatrics
Division Director
General & Community Pediatrics
Cincinnati Children's Hospital Medical Center
[name]
[name]
[contact]

[name], BSN, MSN
Clinical Manager
General & Community Pediatrics
Cincinnati Children's Hospital Medical Center
[name]
[name]
[contact]

[name], MHA
Associate Division Director, Primary Care
General & Community Pediatrics
Cincinnati Children's Hospital Medical Center
[name]
[name]
[contact]

[name]
Staff Physician 1
General & Community Pediatrics
Cincinnati Children's Hospital Medical Center
[name]
[name]
[contact]

[name], BA
Clinical Research Coordinator III
General & Community Pediatrics
Cincinnati Children's Hospital Medical Center
[name]
[name]
[contact]

[name]
Senior Biostatistician
General & Community Pediatrics
Cincinnati Children's Hospital Medical Center
[name]
[name]
[contact]

1. Objective

Our objective is to determine the effectiveness of varied outreach methods (e.g. automated reminder calls/text messages with or without personalized calls/texts, MyChart messaging) to children age 12-14 months, 4 years old, or 6-17 years old who are due for a WCC visit and don't have one scheduled in the next 45 days on the outcomes of appointment scheduling, appointment completion, and receipt of the MMR vaccination.

Background

The Cincinnati Children's Hospital Medical Center Primary Care offices serve as the medical home for over 33,000 children. The Pediatric Primary Care Center (PPCC), Hopple Street Health Center (HPC) and Fairfield Primary Care (FPC) serves an underserved population. Annually, these practices provide over 60,000 visits. Traditional outreach efforts in these offices have included reminder phone calls and/or texts when patients were overdue for well child care (WCC). These efforts were time and resource intensive, as they required personnel to manually complete and document attempts. Additionally, due to high resource needs to accomplish such efforts, there has been no outreach to those 6 years and older.

Numerous studies exist speaking to the efficacy of automated reminder (i.e. notifying parents of needed immunizations) and recall (i.e. notifying parents of overdue immunizations) systems, including text messaging systems.^{1,2,3} Other studies show that the combination of texting and calls proves even more successful in reaching patients.³ These systems are more cost effective and efficient. Differences in the timing of reminders to schedule, as well as the message itself, has been shown to make a difference in the outcomes of reaching patients or scheduling appointments.⁴ However, there remains a need for research that identifies the degree to which combinations of patient reminder systems improve outcomes, especially the outcome of on-time immunization, and how these approaches differ by age of child.¹

Following the COVID-19 pandemic shut-down in which thousands of well child appointments were cancelled or delayed, the importance of a systematic outreach process became more critical. The traditional process is non-standardized and the efficacy of the work is both unknown and expensive. Our objective is to determine the effectiveness of varied outreach methods (e.g. automated reminder calls/text messages with or without personalized calls/texts, MyChart messaging) to children age 12-14 months, 4 years old, or 6-17 years old who are due for a WCC visit and don't have one scheduled in the next 45 days on the outcomes of appointment scheduling, appointment completion, and receipt of the MMR vaccination.

2. Design/Method

To achieve our objective, we will conduct a 2×2 factorial randomized controlled trial. Randomization is justified because 1) it is a rigorous approach to answer our question and 2) we do not have the resources or appointment availability to personally contact every patient who is eligible and have them schedule immediately.

Patient Population:

Patients are eligible for inclusion in this study if they are in one of four eligible groups:

12-14 months AND	4 years AND

• doesn't have a well visit scheduled in the next 45 days• have not yet received 12-month immunizations• have English and/or Spanish as preferred language	
• doesn't have a well visit scheduled in the next 45 days• has not had a well child visit in 365 days• have English and/or Spanish as preferred language

6-11 years AND	12-17 years AND

• doesn't have a well visit scheduled in the next 45 days• has not had a well child visit > 365 days	
• doesn't have a well visit scheduled in the next 45 days• has not had a well child visit in 365 days

• have English and/or Spanish as preferred language	• have English and/or Spanish as preferred language
---	---

Factors under study (levels):

Personal Contacts (12-14 month & 4-year-olds) Trial:

Number of automated messages sent prior to any personal contact attempts (1 vs. 2)

Number of personal contact attempts made by medical assistant (0 vs. 1)

	1 automated message sent	2 automated messages sent
0 personal contact attempt		
1 personal contact attempt		

MyChart Trial:

Families enrolled in MyChart will be selected and randomized into the following groups:

	no message	1 MyChart message sent	2 MyChart messages (e.g. Mon and Thurs)
Low Tailored Message			
High Tailored Message			

Number of messages (0 vs. 1 vs. 2); Type of messages (low tailored message with name only vs. high tailored message with date of last WCC and age included)

Televox (age 6-11yo) Trial:

Patients will be randomized into the following three groups. Patients with MyChart are excluded:

no message	Low Tailored Message 2 automated standard messages sent (e.g. Thu, Fri)	High Tailored Message 2 automated tailored messages sent (e.g. Thu, Fri)
------------	--	---

Televox (age 12-17yo) Trial:

Patients will be randomized into the following three groups:

no message	Low Tailored Message 2 automated tailored messages sent (e.g. Thu, Fri)	COVID Tailored Message 2 automated messages sent (e.g. Thu, Fri)
------------	--	---

Automated Message: Parents indicate their preferred mode of reminder (e.g. call or text message) when they schedule appointments. Cincinnati Children's uses a HIPAA compliant platform called TeleVox to send automated calls and text reminders to parents according to their preferences which are recorded in the Electronic Health Record (EHR).

Here is the script for **low tailored automated messages** that will be sent via call or text:

Clinic	Message 1*	Message 2*
---------------	-------------------	-------------------

HPC	Hi! Hopple misses you! (INSERT FIRST NAME) is due for a checkup. Please call [contact], option 1 to schedule a visit as soon as possible.	Hi! If you haven't already, please call [contact], option 1 to schedule (INSERT FIRST NAME)'s upcoming visit at Hopple.
FPC	Hi! Fairfield misses you! (INSERT FIRST NAME) is due for a checkup. Please call [contact], option 1 to schedule a visit as soon as possible.	Hi! If you haven't already, please call [contact], option 1 to schedule (INSERT FIRST NAME)'s upcoming visit at Fairfield.
PPC	Hi! PPC misses you! (INSERT FIRST NAME) is due for a checkup. Please call [contact], option 1 to schedule a visit or walk in today.	Hi! If you haven't already, please call [contact], option 1 to schedule (INSERT FIRST NAME)'s upcoming visit at PPC or walk in today.

*Message Scripts have been translated into Spanish by Interpreter Services

This is the script for **high tailored automated messages** that will be sent via call or text:

Clinic	Message 1*	Message 2*
HPC	(INSERT FIRST NAME) was seen for a checkup at Hopple on XX/XX/XXXX & is due for a (INSERT CURRENT AGE) checkup. Please call [contact] opt 1.	If you haven't, please call [contact] opt 1 to schedule (INSERT FIRST NAME)'s (INSERT CURRENT AGE) checkup at Hopple. Stay up to date!
FPC	(INSERT FIRST NAME) was seen for a checkup at Fairfield on XX/XX/XXXX & is due for a (INSERT CURRENT AGE) checkup. Please call [contact] opt 1.	If you haven't, please call [contact] opt 1 to schedule (INSERT FIRST NAME)'s (INSERT CURRENT AGE) checkup at Fairfield. Stay up to date!
PPC	(INSERT FIRST NAME) was seen for a checkup at PPC on XX/XX/XXXX & is due for a (INSERT CURRENT AGE) checkup. Please call [contact] opt 1 to schedule or walk in today.	If you haven't, please call [contact] opt 1 to schedule (INSERT FIRST NAME)'s (INSERT CURRENT AGE) checkup at PPC or walk in today. Stay up to date!

This is the script for **COVID tailored automated messages** that will be sent via call or text:

Clinic	Message 1*	Message 2*
HPC	Hi! Hopple misses you! (INSERT FIRST NAME) is due for a checkup. Please call [contact], option 1 to schedule a visit as soon as possible. COVID vaccine is available if interested.	Hi! If you haven't already, please call [contact], option 1 to schedule (INSERT FIRST NAME)'s upcoming visit at Hopple. COVID vaccine is available if interested.
FPC	Hi! Fairfield misses you! (INSERT FIRST NAME) is due for a checkup. Please call [contact], option 1 to schedule a visit as soon as possible. COVID vaccine is available if interested.	Hi! If you haven't already, please call [contact], option 1 to schedule (INSERT FIRST NAME)'s upcoming visit at Fairfield. COVID vaccine is available if interested.
PPC	Hi! PPC misses you! (INSERT FIRST NAME) is due for a checkup. Please call [contact], option 1 to schedule a visit or walk in today. COVID vaccine is available if interested.	Hi! If you haven't already, please call [contact], option 1 to schedule (INSERT FIRST NAME)'s upcoming visit at PPC or walk in today. COVID vaccine is available if interested.

*Message Scripts have been translated into Spanish by Interpreter Services

Personal Contact Attempts: Medical assistant(s) will use the following message/script to personally contact families via text message and then phone call.

Clinic	Text Message*	Call Script*
HPC	Hi, this is [Staff First Name] from Hopple St. Health Center. [Pt first name] is due for a check up. I'll call in a day or two to help	Hi, this is [Staff First Name] from Hopple St. Health Center. I noticed that [Child's First

	
schedule that appointment or you can call [contact], option 1 to schedule.
	
Name] is due for a check up. Can I schedule that for you right now?
 
Alternate script for leaving a voice message: Hi, this is [Staff First Name] from Hopple St. Health Center. I noticed that [Child's First Name] is due for a check up. Sorry I missed you. Please call [contact], option 1 to schedule your appointment.

FPC	
Hi, this is [Staff First Name] from Fairfield. [Pt first name] is due for a check up. I'll call in a day or two to help schedule that appointment or you can call [contact], option 1 to schedule.
	
Hi, this is [First Name] from Fairfield. I noticed that [Child's First Name] is due for a check up. Can I schedule that for your right now?
 
Alternate script for leaving a voice message: Hi, this is [First Name] from Fairfield. I noticed that [Child's First Name] is due for a check up. Sorry I missed you. Please call [contact], option 1 to schedule your appointment.

PPC	
Hi, this is [Staff First Name] from PPC. [Pt first name] is due for a check up. I'll call in a day or two to help schedule that appointment or you can walk in today to have your child seen! You can also call [contact], option 1 to schedule.
	
Hi, this is [First Name] from PPC. I noticed that [Child's First Name] is due for a check up. Can I schedule that for your right now?
 
Alternate script for leaving a voice message: Hi, this is [First Name] from PPC. I noticed that [Child's First Name] is due for a check up. Sorry I missed you. Please call [contact], option 1 to schedule your appointment or walk in today to have your child seen.

*Scripts have been translated into Spanish versions by Interpreter Services

Response variables (outcomes):

- Appointment **was scheduled** within 2 weeks of intervention (Y/N) (date of actual appointment may be greater than 2 weeks from intervention)
- Appointment **was completed** within 8 weeks of intervention (Y/N). Appointment completed within 8 weeks of randomization will be used for group who does not receive any intervention.
- (Primary Outcome) Receipt of MMR by 15 months of age or receipt of 2nd MMR dose by 3 months after randomization (Y/N)
- Receipt of 1st COVID vaccination (ages 12-17 years) within 8 weeks of first intervention (Y/N)
- Family member receipt of COVID vaccination in our health system within 8 weeks of first intervention

Blocking: (controlling for factors that might influence the outcome)

- Age (12-14 months, 4 years)
- Clinic location (PPC, HPC, FPC)

Personal Contacts (12-14 months & 4-year-olds) Trial:

Randomization: Eligible patient will be identified by running a report in the electronic health record (EHR). We will run this report, stratified by clinic location, and randomly assign patients into one of the four groups created by our 2 X 2 design. Groups will receive their assigned intervention in one of four successive weeks with the sequence randomly assigned (see table below).

Replication: We will conduct a total of 3 trials, repeating the randomization procedure every 4 weeks to identify children who become eligible: Weeks 1-4 = trial #1, weeks 5-8 = trial #2, weeks 9-12 = trial #3.

	1 automated message sent	2 automated messages sent
--	---------------------------------	----------------------------------

0 personal contact attempt	Message sent on Thu (weeks 3, 5, 10)	Message sent on Thu & Fri (weeks 4, 6, 12)
1 personal contact attempt	Above plus attempt Mon – Fri of following week (weeks 2, 7, 11)	Above plus attempt Mon – Fri of following week (weeks 1, 8, 9)

MyChart and Televox Trials (6-17 years old):

Randomization: Eligible patients will be identified by running a report in the electronic health record (EHR). We will run this report, stratified by clinic location, and randomly assign patients into one of the study groups as described above. Groups will receive their assigned intervention in one of four successive weeks with the sequence randomly assigned (see table below).

We will randomize children who are eligible and implement interventions for each trial : Weeks 1-3 = Televox Trial 12-17yo, Weeks 4-7 = Televox Trial 6-11yo, Weeks 8-10 = MyChart Trial.

MyChart Trial:

	no message	1 MyChart message sent	2 MyChart messages (e.g. Mon and Thurs)
Standard Message	No intervention	Week A	Week B
Tailored Message		Week A	Week B

Televox (6-11yo) Trial:

no message	Low Tailored Message 2 automated standard messages sent (e.g. Thu, Fri) (weeks C, C)	High Tailored Message 2 automated tailored messages sent (e.g. Thu, Fri) (weeks D, D)
-------------------	---	--

Televox (12-17yo) Trial:

no message	Low Tailored Message 2 automated tailored messages sent (e.g. Thu, Fri) (week A)	COVID Tailored Message 2 automated messages sent (e.g. Thu, Fri) (week B)
-------------------	---	--

Of note, automated messages and/or personal contact attempts will not be completed if the parent schedules an appointment after being randomized but before receiving the intervention.

Covariates for logistic regression: (factors that might influence the outcome if not be balanced across groups)

1. Child age at the time of randomization (rationale: visits are less frequent for children age 4 years)
2. Parent preference for call vs. text mode of contact (rationale: calls may be more likely to get blocked than texts)
3. Parent with activated MyChart account (Y/N) (rationale: not dependent on calling scheduling center to make appointment)
4. Access to appointment: Number of days to 3rd next available appointment at patient's clinic at time their first automated message is sent
5. Patient receipt of any past immunizations (Y/N) (rationale: vaccine refusing parents will be unlikely to change even if they return for well child check)

6. School-age vs. adolescent patient age (rationale: adolescents less likely to get yearly check-ups)
7. Historical no-show rate
8. Community rates of COVID based on 7 day moving average.

Power/Sample Size

Personal Contacts (12-14 month & 4-year-olds) Trial:

We based our hypotheses (see table, below) on a systematic review's pooled estimates of effect size for automated messages and personalized calls finding 37% and 40% of children, respectively, completed immunizations.¹ Because of the significant cost involved in making personal contacts, the minimal difference in outcome that would make it worth the effort is high.

Hypotheses	% of children who receive MMR by 15 months of age	
	1 automated message sent	2 automated messages sent
0 personal attempts	20% ^C	35% ^B
1 personal attempt	50% ^A	65% ^{AB}

We calculated sample size needed per group to detect a difference for each of the contrasts below with alpha of 0.05 and power of 80%.

Contrast	Sample Size per Group
A vs C	36
B vs C	136
A vs. B	167
A vs. AB	167
B vs. AB	40
C vs. AB	16

To fully power the 2 X 2 factorial trial, we estimate needing 167 per group X 4 groups = 668 total subjects. There are currently 712 children eligible for the study. More will become eligible every month so we expect to far exceed the required sample size after 3 replications. If needed, we could increase the number of replications of the trial to reach the targeted sample size. We acknowledge that we are not powered to precisely estimate any interactions between interventions.

MyChart Trial:

In hypothesis testing for 0 message vs. 1 message vs. 2 messages, we will do the testing in a fixed sequence - test 2 messages vs. 0 message first, only if it is significant then test 2 messages vs. 1 message, thus the type I error rate of 0.05 is retained. Since the hypothesis testing of 2 messages vs. 0 message would be considered easier to achieve than the hypothesis testing of 2 messages vs. 1 message, the power analysis for this trial should be based on the design of (standard message vs. tailored message) by (1 message vs. 2 messages). We based our hypotheses (see table, below) on previous work indicating approximately 20% WCC appointment completion on automated text reminders. We anticipate that a tailored message increases the WCC appointment completion rate by another 10%.

Hypotheses		% of children complete WCC within 8 weeks	
		1 automated message sent	2 automated messages sent
Standard Message	2%	10% ^C	20% ^B
Tailored Message		20% ^A	30% ^{AB}

We calculated sample size needed per group to detect a difference for each of the contrasts below with alpha of 0.05 and power of 80%.

Contrast	Sample Size per Group
A vs C	199
B vs C	199
A vs. AB	293
B vs. AB	293
C vs. AB	62

We assume no difference between A vs. B and thus not consider powering the comparison between these two groups, but we will explore non-inferiority analysis for this comparison in data analysis. To fully power the above contrasts, we estimate needing 293 per group X 4 groups = 1172 subjects. Adding 293 in the zero message group, we would need a total of 1465 subjects. There are currently 1000 children eligible for the study. More will become eligible every month so we expect to exceed the required sample size after 2 replications. If needed, we could increase the number of replications of this trial to reach the targeted sample size. We acknowledge that we are not powered to precisely estimate any interactions between interventions.

Televox (6-11yo) Trial:

We calculated sample size based on the following hypotheses:

% of children complete WCC within 8 weeks		
no message	2 Low Tailored Messages	2 High Tailored Messages
2%	20%	30%

With alpha of 0.05 and power of 80%, to fully power the contrasts between the above groups, we need 293 per group X 3 groups=879 subjects. Currently there are 2500 kids eligible, so we expect to reach the targeted sample size.

Televox (12-17yo) Trial:

We calculated sample size based on the following hypotheses:

% of children complete WCC within 8 weeks		
no message	2 Low Tailored Messages	2 COVID Tailored Messages
2%	30%	40%

With alpha of 0.05 and power of 80%, to fully power the contrasts between the above groups, we need 356 per group X 3 groups=1068 subjects. Currently there are 1100 kids eligible, so we expect to reach the targeted sample size.

Analysis

We will conduct descriptive analyses to characterize the participants in terms of demographics and other potential covariates in consideration (child age group, parent's preference for call vs. text mode of contact, whether parent had activated MyChart account, access to appointment, whether patient receipt of any past immunizations, historic no show rate, and community rates of COVID). We will use chi square tests to examine whether participants in the 4 groups are similar in these characteristics.

For the Personal Contact (12-14 mo & 4 years old) trials, we will conduct intent-to-treat analyses using logistic regression models (without adjusting for covariates) for each of our three binary outcomes: completed appointment

within 2 weeks, completed appointment within 8 weeks, receipt of MMR by 15 months of age or receipt of 2nd MMR by 3 months after randomization. We will do pair-wise comparison among the 4 groups and adjust p value of each comparison for multiplicity. If participants in the 4 groups differ on potential covariates, we will conduct additional analyses adjusted for these variables.

For the MyChart and Televox Trials (6-17 years old), we will conduct intent-to-treat analyses using logistic regression models (without adjusting for covariates) for each of the binary outcomes: scheduled appointment within 2 weeks, completed appointment within 8 weeks, receipt of 1st dose of COVID vaccination (age 12-17 years) within 8 weeks, family member receipt of COVID vaccination within 8 weeks. We will do pair-wise comparison among the treatment groups and adjust p value of each comparison for multiplicity. If participants differ in potential covariates across treatment groups, we will conduct additional analyses adjusted for these variables. We will explore non-inferiority analysis for comparison the two groups that are expected to have similar appointment scheduled and completion rate in the MyChart trial.

We will also conduct per-protocol analyses according to the interventions actually received by the participants, recognizing that actual intervention received could be different from initial randomized intervention. For example, a parent allocated to group A might schedule an appointment after receiving the automated message and therefore would not receive a personalized contact attempt. In addition, we may explore potential interaction between the two interventions as a secondary analysis. All analysis will be conducted using SAS version 9.4.

Duration

The study will begin upon IRB approval and continue through December 31, 2022. During this time, we will discuss the significance of data, potential future projects and dissemination of results.

Process of Obtaining Consent

For this study, we request a waiver of consent due to the minimal risk to participants involved. Given the population we are attempting to contact using the various outreach methods has missed appointments, it would not be possible to obtain prospective consent. That said, we will honor parent preferences for how they receive automated messages. Collected data about appointment attendance and MMR vaccination status is already being documented in the EHR, and the collection of data will not affect the rights and welfare of subjects.

We request waiver of consent such that there is (1) potential, minimal, risks to the participant (see below), (2) de-identification of PHI, and (3) participation in the study will not affect current/future care received through CCHMC.

All identifying information will be removed once data collection is complete. Data will be kept securely on a CCHMC computer that is password protected. Any hard copies of data will be locked in a private office.

Facilities and Performance Sites

Data analysis will be done on the Main Campus of CCHMC and at the CCHMC primary care offices (PPCC, HPC, FPC, and SBHCs).

Potential Benefits

The results of this study will aid CCHMC pediatric primary care centers in improving and redesigning an outreach system to children behind on necessary preventative services who have gaps in needed primary care. It will identify the most effective ways to reach, engage, and schedule patients for care when appropriate. This will enable the primary care offices to allocate the appropriate amount of resource to outreach efforts moving forward, ensuring high risk children receive reminders for care.

Potential risks, discomforts, inconveniences, and precautions

The only significant risks are breach of confidentiality and potential discomfort/inconvenience associated with receiving texts or phone calls indicating that care gaps exist for a child. As noted above, personal health information (PHI) will be obtained via the electronic medical record. After obtaining this information, patients will be de-identified in the created database and securely stored.

Risk/Benefit analysis

While immediate benefit to any given individual or family is unknown, this study involves minimal risk.

Outreach Methods Study Protocol

Version 1.1, 1/14/22

pg. 9

Cost of Participation

There is no cost for participation.

Payment for Participation

There is no reimbursement for participation.

Request for HIPAA Waiver

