Official Title of the study: **Effect of Varied Outreach Methods on Appointment Scheduling, Appointment Completion, and Receipt of MMR Vaccination**

NCT number: **NCT04567342**

Document name: **Statistical Analysis Plan**

Date of the document: **7/31/2023**

The results of the Outreach Methods study will be assessed as described in this document. This statistical analysis plan begins with an overview of the key components of the study, including its design, objectives, and outcomes measures. This is followed by a detailed description of the statistical analyses that will be utilized to address study hypotheses.

1. Overview of study: This study used a 2x2 factorial randomized control trial to test the impact of automated text/telephone messages and personal contact attempts on well child care (WCC) scheduling and completion and receipt of MMR vaccine. We randomized eligible patients to 1 of 4 groups: 1 automated message (Group 1), 2 automated messages (Group 2), 1 automated message plus personal contact attempts (Group 3), or 2 automated messages plus personal contact attempts (Group 4). We generated random allocation sequence stratified by clinic location using block randomization (with a block size of 4). Based on sample size calculations, we planned to enroll a minimum of 668 subjects overall aged 12-14 months old and 4 years old that met eligibility criteria based on data obtained from the electronic health record (EHR) from three academic pediatric primary care practices.

1.1 Study Objective: Test the effectiveness of text/telephone outreach messages and personal contact attempts on well child care (WCC) scheduling and completion and receipt of MMR vaccine.

Working hypothesis: Twenty percent of patients in Group 1, 35% of patients in Group 2, and 50% of those in Group 3, and 65% of those in Group 4 would receive the MMR vaccine by 15 months of age (for children who were 12-14 months old) or receipt of the second MMR dose by 3 months after first intervention (for children 4 years old).

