1.2 Outcome measures

Primary

- Receipt of MMR by 15 months of age (for children who were 12-14 months old) or receipt of the second MMR dose by 3 months after first intervention (for children 4 years old).
 - Receipt of MMR (yes or no) based on electronic health record documentation

Secondary

- Well-child visit scheduled within 2 weeks of receiving first intervention
 - Appointment scheduled (yes or no) based on electronic health record documentation
- Well-child visit completed within 8 weeks of receiving first intervention
 - Appointment completed (yes or no) based on electronic health record documentation

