2.3 Statistical Report Contents

The following section outlines the contents of the final statistical analysis. For all analyses, subjects who are enrolled in the study and are eligible will be analyzed in the groups to which they were allocated.

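### Four-year-olds enter the Personal Contacts trial without a check that the second MMR dose is outstanding, and the primary outcome does not say how an earlier dose is scored

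*Protocol*

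**What the plan says.** The Protocol's section 2 (Patient Population) sets different kinds of entry rule for the two age groups in the Personal Contacts trial. At 12-14 months the vaccine must be outstanding: the child must "have not yet received 12-month immunizations". At 4 years the rules are no well visit scheduled in the next 45 days, language preference, and that the child "has not had a well child visit in 365 days". No vaccine criterion appears. This follows the stated objective, which targets children "who are due for a WCC visit and don't have one scheduled in the next 45 days", but the primary outcome is MMR receipt.

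For 4-year-olds the Protocol (Response variables) defines that outcome as "receipt of 2nd MMR dose by 3 months after randomization (Y/N", and SAP 1.2 as "receipt of the second MMR dose by 3 months after first intervention (for children 4 years old". Both set an end to the window; neither sets a beginning or says how a dose given before randomization is scored.

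SAP 2.3 states that "subjects who are enrolled in the study and are eligible will be analyzed in the groups to which they were allocated". The baseline vaccine variables are receipt of any past immunization (Protocol, covariate list) and absence of past DTaP (SAP 2.3.1). Neither identifies a child who already has a second MMR dose, and SAP 2.2.2 on missing data does not address the case.

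**The concern.** A 4-year-old whose second dose is already on record cannot change outcome, whatever outreach the family receives. The child is a fixed success if the outcome is read literally, or a fixed failure if only new doses count. The plan does not say which, and the choice affects the risk ratio, which SAP 2.3.2 makes the primary effect measure.

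To the extent that such children are enrolled, the primary comparison loses power, and the reported effect describes a mixture of children due and not due for the vaccine. The two readings would also give different risk ratios from the same data.

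**Working it through.** **Inputs.** The planned rates are 20% (one message, no personal contact: C), 35% (two messages: B), 50% (one message plus contact: A) and 65% (both: AB), from Protocol Power/Sample Size and SAP 1.1. Alpha is 0.05, power 80% and n = 167 per group (Protocol). Tests are two-sided (SAP 2.3.2).

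**Reproducing the plan.** With unpooled variance, n = (1.96 + 0.8416)² × [p1(1−p1) + p2(1−p2)] / (p1−p2)². For A vs B this is 7.849 × (0.2275 + 0.25) / 0.0225 = 166.6, or 167. The same formula returns 36, 136, 167, 167, 40 and 16 for the six contrasts, matching the Protocol.

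**Dilution model.** Let s be the share of all randomized children who already have dose two, and p the rate among the rest.
- Earlier dose scored Yes: the rate becomes p + s(1−p). The risk difference is multiplied by (1−s) and the risk ratio falls.
- Earlier dose scored No: the rate becomes (1−s)p. The risk difference is again multiplied by (1−s); the risk ratio is unchanged.
- Excluded: the rates stay at p and n becomes 167(1−s).

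Power = Φ(|difference| / √{[p1(1−p1) + p2(1−p2)]/n} − 1.96).

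**The share.** The documents give no value for s. It is the fraction of the sample aged 4 times the fraction of those already vaccinated. As an assumption, if half the sample is aged 4 and 5%, 10% or 20% of them have dose two, s is 2.5%, 5% or 10%.

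**Example, s = 5%, scored Yes.** B: 0.35 + 0.05 × 0.65 = 0.3825. A: 0.50 + 0.05 × 0.50 = 0.525. The difference is 0.1425 and the ratio 1.37. The standard error is √[(0.2362 + 0.2494)/167] = 0.0539, and power is Φ(2.643 − 1.96) = 75.3%.

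**A vs B (50% vs 35%), 167 randomized per group:**

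| s | Scored Yes: rates; RR; power | Scored No: rates; RR; power | Excluded: n; RR; power |
|---|---|---|---|
| 0 | 50.0 vs 35.0; 1.43; 80.1% | same | 167; 1.43; 80.1% |
| 2.5% | 51.3 vs 36.6; 1.40; 77.7% | 48.8 vs 34.1; 1.43; 78.3% | 162.8; 1.43; 79.1% |
| 5% | 52.5 vs 38.3; 1.37; 75.3% | 47.5 vs 33.3; 1.43; 76.5% | 158.7; 1.43; 78.1% |
| 10% | 55.0 vs 41.5; 1.33; 70.3% | 45.0 vs 31.5; 1.43; 72.7% | 150.3; 1.43; 75.8% |

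**Other contrasts.** For AB vs A (65% vs 50%), scored Yes, power is 78.3%, 76.5% and 72.7% at the same shares. The two 30-point contrasts (A vs C, AB vs B) keep more than 99% power throughout.

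**Enrolment needed to hold 80%** for A vs B with these children left in and scored Yes: 177, 188 and 212 per group.

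**The case against.** The strongest reply is that the documents do not show that any such child was enrolled. The 365-day rule is a partial screen: a child still aged 4 with no well visit in 365 days has had no recorded well visit since turning 4. What remains is a second dose given before age 4, at another kind of visit, or elsewhere. This stands, and so the size is unknown.

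Second, the outcome of an outreach trial may be meant as a dose received during follow-up. The risk ratio is then not diluted. This stands as a possible reading, but the wording does not settle it, and the loss in risk difference and power remains.

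Third, the power loss is conditional. SAP section 1 treats 668 as a minimum. The Protocol counts 712 children already eligible, expects more and allows further replications. At 712/4 = 178 per group, A vs B scored Yes has 80.3% power at s = 2.5% and 77.9% at 5%.

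Fourth, SAP 1.1 attaches the planned rates to the whole composite outcome, so they may already include earlier vaccinees; the Protocol's planning table names only MMR by 15 months. If they do, power at 167 is 80% as planned. Restriction would still help. At s = 5%, the rates among children still due would be (0.35−0.05)/0.95 = 0.316 and (0.50−0.05)/0.95 = 0.474. With 158.7 per group, power is Φ(0.158/0.0542 − 1.96), about 83%.

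Finally, targeting children due for a visit is a legitimate design choice. That does not remove the need to say how an earlier dose is scored.

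**Conclusion.** The gap is real. The 4-year group has no dose-two check at entry, the outcome window has no start, and nothing in the analysis plan identifies earlier vaccinees. Under either reading the risk difference shrinks by the factor (1−s); under the literal one the risk ratio also moves toward 1. The figures for A vs B assume s between 2.5% and 10%, planned rates that describe children still due, and exactly 167 per group. Restricting to children still due gives more power than leaving the others in, under both readings, and keeps the planned risk ratio.

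A reader might infer that already-vaccinated children are present in number and have diluted the effect, or that power is below 80%. The documents support neither as fact: they give no count, the 365-day rule removes some such children, and enrolment above 167 per group would offset small shares. Nor is this confounding, since randomization balances earlier vaccination on average.

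**What to change.** In SAP 1.2 and 2.3.2, define the 4-year primary outcome as a second MMR dose dated after randomization and by 3 months, among children with no second dose recorded in the EHR at randomization. The same sentence should settle the end of the window, which the Protocol counts from randomization and the SAP from first intervention. Report the number already vaccinated by arm. Keep all randomized children in the well-visit outcomes, and run the MMR analysis on all randomized children as a sensitivity analysis with the scoring of earlier doses stated.

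Because the restriction uses a characteristic fixed before randomization, it preserves the randomized comparison. If outcomes have already been analyzed, label the restricted analysis as added afterwards. A new eligibility criterion would serve no purpose: SAP 2.2.1 gives a study end date of 8/6/21 and the SAP is dated 7/31/2023.

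The cost is one baseline EHR field and a short SAP change. The downside is that the primary denominator falls by the share already vaccinated, for example from 167 to about 150 per group at 10%.
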